8.0 Research Question and Objectives

The objective of this study is to assess the effect of adalimumab on health and disability outcomes in patients with the immune-mediated inflammatory diseases of rheumatoid arthritis. The effect of adalimumab on health and disability outcomes in these patients will be assessed by the primary outcome measure which is the change in Health Assessment Questionnaire Disability Index (HAQ DI) score at 24 weeks after the initiation of adalimumab. The HAQ DI is selected as the primary point as it is commonly used to assess improvements in physical function in RA clinical trials and recommended by the US Food and Drug Administration (FDA) guidance on RA treatment development (3, 4).

In addition, the HAQ-DI has been utilized as a predictor variable in investigations of productivity (5). The HAQ-DI has been demonstrated to be significantly correlated with work-related measures such as work capacity, household work performance, work task performance, and work disability (6-9). In addition, the effect of adalimumab will also be assessed by the secondary outcome measures which are changes to the WPAI, EuroQol 5 dimension (EQ-5D) score, and Short Form 36-Item Health Survey (SF-36) domain scores at 12 and 24 weeks after the initiation of adalimumab in RA.

9.0 Research Methods

9.1 Study Design

This study is designed as a prospective, observational study to assess the effect of adalimumab on health-related QoL and work productivity in patients with RA in Korea in clinical practice.

Note: This study is non-interventional and the subjects/investigators will follow the current clinical practice in each site and also the routine clinical follow up as determined by the treating physician.

RA patients will be recruited from within the clinical settings of each rheumatologist participating in the study. Approximately 89 patients diagnosed with RA that meet the inclusion and exclusion criteria will be enrolled at approximately 9 sites in Korea.

To assess health and disability outcomes, the HAQ DI will be assessed at baseline, Week 12 and Week 24 after treatment initiation with adalimumab. In addition, other PROs of work activity and well-being, including the WPAI, EQ-5D, and SF-36, will also be assessed.

The patients identified by the recruiting investigators (specialty dependent on country/region; e.g. rheumatologist, internists, general practitioners, etc.) based on the study selection criteria will complete a set of patient questionnaires on QoL, functioning, work productivity, treatment satisfaction, impression of change and HCRU. Data will be captured at baseline (D0), Week 12 and Week 24.

The HCRU will also be collected. This includes surgical procedures, hospitalizations, bed days in hospital, physician consultations etc. Costs will be assigned based on the HCRU using standardized costs for each participating countries.

Subjects may discontinue adalimumab treatment at any time during study participation. Subjects that end study participation early will have a Termination Visit. All subjects will have a follow-up phone call approximately 70 days after the last administration of adalimumab to obtain information on any new or ongoing AEs.

This protocol requires all SAEs and AESIs as outlined in protocol section 11.0 to be actively solicited. The safety profile of adalimumab which has over 3.5 million patient years of post-marketing exposure is stable and well established; non-serious events will not be actively solicited as these events are not likely to contribute to the further understanding of the safety profile of the product. Any non-serious AEs will be collected as spontaneous reports if AbbVie is notified.

As this is a postmarketing observational study, Abbvie is NOT involved in the product supply since the drug is being used according to the approved market label and is to be prescribed by the physician under usual and customary practice of physician prescription. This study is non-interventional and the subjects/investigator will follow the current clinical practice in each site. Not additional task will be required other than current practice to keep the data as “real world data collect.

Primary Endpoint

Change in HAQ DI score at 24 weeks after the initiation of adalimumab(observed population). This change will be summarized as the mean and 95% confidence interval and will be tested with a paired t-test.

Secondary Endpoint Analysis

- Number and percent of patients achieving a clinically meaningful improvement on the HAQ DI, as defined by a -0.22 point improvement or greater, at weeks 12 and 24 after the initiation of adalimumab (observed population).

Additional Secondary Endpoint Analysis

- Change in HAQ DI score at 24 weeks after the initiation of adalimumab (observed population), compared with those patients not continuing on adalimumab (non-observeds). The mean changes in these two groups will be compared using an independent t-test.
- Healthcare resource utilization will be described using number and percentage within each category (number of consultations, number of procedures received, number of surgeries, number of hospitalizations and length of stay, number of concomitant medications)
- Associations between disease severity and PROs
- Associations between change in disease severity and change in PROs

- Change in other patient reported outcomes (SF-36 domain scales, EQ-5D Index, WPAI total lost productivity) at weeks 12 and 24 after the initiation of adalimumab (observed population). These changes will be summarized as the means and 95% confidence intervals and will be tested with paired t-tests.
- Change in patient satisfaction questions at weeks 12 and 24 after the initiation of adalimumab (observed population). These changes will be summarized as number and percentage of each response and compared with Kruskal-Wallis test. Satisfaction will also be dichotomized and analysed over time with Cochrane-Armitage test for trends.

All instruments used in the study are translationally validated for the country language.

9.1.1 Schedule of Events

Table 1 Study Activities (Day 1/Baseline Through 6 months)

	Study Activity	Baseline ^a	Week 12 (V2) ± 7 days	Week 24 (V3) ± 7 days	Early Termination / Drop out
Clinician Packet	Inclusion/exclusion form	X			
	Clinical history/patient demographics	X			
	Comorbidities	X			
	DAS28 (ESR) or DAS28 (CRP)	X	X	X	X
Patient Packet	EuroQoL 5-Dimension (EQ-5D)	X	X	X	X
	Short Form 36-Item Health Survey (SF-36)	X	X	X	X
	Health Assessment Questionnaire (HAQ)	X	X	X	X
	Work Productivity and Activity Impairment Questionnaire (WPAI)	X	X	X	X
	Healthcare Resource Utilization (HCRU)	X	X	X	X
	Patient Global Impression of Change (PGIC)		X	X	X
	Patient Treatment Satisfaction Questions	X	X	X	X
	Adverse events (including malignancy)	X	X	X	X

a. The Baseline visit date will serve as the reference for all subsequent visits. A ± 7 day window is permitted around scheduled study visits.

9.2 Setting

The study will take place in single country (Korea) with multiple centers. The study sites will be identified and selected by AbbVie. The study population shall comprise of male

and/or female patients who are attending a routine clinical visit and meet all of the inclusion criteria and none of the exclusion criteria. Overall, approximately 89 subjects with clinically diagnosed RA are planned to be enrolled in the study at up to 9 sites.

The recruiting investigators will select potentially eligible patients from consecutive visits within their clinic based on the inclusion and exclusion criteria (Section 9.2.1 and Section 9.2.2). It is the responsibility of each physician to ask every consecutive patient who meets the inclusion criteria of the study to participate to avoid selection bias, and if investigators hold different types of clinics (e.g. routine visit clinics versus emergency clinics), only patients visiting their routine clinics will be used for patient selection. Site personnel should thoroughly assess the eligibility criteria and evidence of this should be stored with the source documentation at site.

Where there is any deviation from the inclusion/exclusion criteria, the patient should be excluded from the study.

9.2.1 Inclusion Criteria:

Patients meeting all of the following inclusion criteria at baseline will be included:

1. Subject has a diagnosis of RA as defined by the 1987 revised ACR classification criteria and/or the ACR/ the European League against Rheumatism (EULAR) 2010 classification criteria (any duration since diagnosis)
2. Male or female subjects ≥ 18 years of age (local definition according to adalimumab label) who is in compliance with eligibility for adalimumab based on the local label
3. Patients with moderate to severe RA defined as DAS28 (ESR) or DAS28 (CRP) >3.2
4. Biologically treatment naïve and initiated adalimumab at baseline visit
5. Availability of clinical data of the previous 12 weeks prior to baseline
6. Ability to self-complete patient questionnaires
7. Subject must be able and willing to provide written informed consent and comply with the requirements of this study protocol

9.2.2 Exclusion Criteria:

Patients meeting any of the following exclusion criteria at baseline will be excluded:

1. Patients who are pregnant or breast feeding at enrolment or wish to become pregnant in the next 24 weeks
2. Participation in any RA-related clinical trial at the time of enrolment, at baseline or at any point during the past 24 weeks prior to baseline

3. Patients, who in the clinician's view, may not be able to accurately report their QoL or prior resource utilization
4. Patients, who in the clinician's view, may not be able to adhere to adalimumab therapy over 24 weeks

9.2.3 Investigator Selection Criteria

Selection of investigators will be made based on qualification by training and experience. AbbVie will provide IMS with a list of clinicians that would be able to assist in recruiting in a timely manner. IMS will contact each clinician to obtain their participation in the study and provide an expected number of patients to be enrolled from that clinic. The ethical review boards recognized by the respective participating sites are required to review and approve the study and patient informed consent.

9.2.4 Study Procedures

The study procedures outlined in Table 1 will be discussed in detail in this section with the exception of adverse events procedures (discussed in Section 11.0).

9.2.4.1 Informed Consent

In local languages will be given to every patient participating in the study before data collection commences. The recruiting clinicians or their representative(s) will provide each patient with the ICF to sign which includes consent to use the data for publication and information including their right to withdraw from the study without penalty or change in medical care the patient is otherwise entitled to.

[figure not shown]
9.2.4.2 Patient Assignment

Once the recruiting clinician has obtained the subject's authorization to release medical information and written consent to participate in the study, the clinician will be asked to complete an inclusion and exclusion form (Appendix B) for patients, thus confirming the patient's eligibility to participate in this study.

Each participating patient will be assigned a 3-digit patient identification number. The numbers should be assigned in sequential, ascending order per site as shown below:

- Site ID; and

- Patient ID: First eligible patient number will be 001, and then the second patient number would be 002

9.2.4.3 Investigator Recruitment

AbbVie will provide IMS with a list of clinicians that would be able to assist in recruiting in a timely manner. IMS will contact each clinician to obtain their participation in the study and provide an expected number of patients to be enrolled from that clinic. The ethical review boards recognized by the respective participating sites are required to review and approve the study and patient informed consent.

9.2.4.4 Study site monitoring

As the study entails patients completing PRO questionnaires and clinicians completing case report forms (CRFs), there is not a need for on-site monitoring visits. IMS will closely track enrolment progress for bi-monthly reporting. IMS will work closely with the study coordinator at each site to ensure they check the forms when returned from the patients and physicians (e.g., all questions were answered). IMS will also be available to answer questions and follow up with the sites if the recruitment process is slow or if there are any errors on the forms. Periodic phone follow-up will be conducted to ensure data collection completeness and quality.

9.2.4.5 Patient Selection

The recruiting investigators will select potentially eligible patients from consecutive visits within their clinic based on the inclusion and exclusion criteria (Section 9.2.1 and Section 9.2.2). It is the responsibility of each physician to ask every consecutive patient who meets the inclusion criteria of the study to participate to avoid selection bias, and if investigators hold different types of clinics (e.g. routine visit clinics versus emergency clinics), only patients visiting their routine clinics will be used for patient selection. The intent is to enroll patients who have been prescribed adalimumab upon the physicians' own discretion. This study is non-interventional and the subjects/investigator will follow the current clinical practice in each site. Not additional task will be required other than current practice to keep the data as "real world data collect."

9.2.4.6 Data Collection

IMS will coordinate data collection with each site. At study initiation (Baseline, D0), patients will be asked to provide their written informed consent. The patient then will complete the study questionnaires in paper form. At all follow up visits (week 12 and 24), the patient will complete the study questionnaires while waiting for their appointment at their clinic, approximately 30 minutes before they visit their physicians. It is important that they complete the questionnaires prior to speaking with their clinician during the visit, as the clinician feedback might impact patient perceptions measured by the PRO instruments.

Patients must complete the survey by themselves without help from anyone. However, for patients who physically have difficulty filling out the questionnaires, help is allowed as long as there are no suggestions or discussion from the helpers. In addition, physicians will also be asked to complete a clinical CRF in paper form based on the patient's medical records at baseline, 12 weeks, and 24 weeks. The CRF completed by physicians will be returned to the study coordinator/nurse at each site as well.

All data filled in by the patient and physician will be collected at each site and returned directly to IMS. The data collection time is expected to be 10-13 months.

All patient and clinician data will be handled preserving confidentiality.

9.2.4.7 Study Documents

Clinical case report form (CRF)

The clinical CRF will document the patient's current status (moderate, severe RA), Disease Activity Score in 28 joints (DAS28), prior and current treatments and other relevant clinical and demographic data to be used in segmenting the population during analysis.

To calculate the DAS28 the physician or specialist nurse will:

1. Count the number of swollen joints (out of the 28)
2. Count the number of tender joints (out of the 28)
3. Take blood to measure the erythrocyte sedimentation rate (ESR) or C reactive protein (CRP); the latest measurement in the medical records may also be used if a blood draw is not standard for that visit
4. Ask the patient to make a 'global assessment of health' which will be indicated by marking a 10 cm line between very good and very bad

The physician or specialist nurse will then mark each component score on the CRF and the DAS28 score if calculated (an online scoring calculator for the DAS28 can be found at <http://www.das-score.nl/das28/DAScalculators/dascalculators.html>).

The DAS28 will be scored using the following formula:

$$\text{DAS28 ESR} = 0.56 * \text{sqrt}(\text{tender28}) + 0.28 * \text{sqrt}(\text{swollen28}) + 0.70 * \ln(\text{ESR}) + 0.014 * (\text{Global assessment of Health in cm})$$

$$\text{DAS28 CRP} = 0.56 * \text{sqrt}(\text{tender28}) + 0.28 * \text{sqrt}(\text{swollen28}) + 0.36 * \ln(\text{CRP}) + 0.014 * (\text{Global assessment of Health in cm}) + 0.96$$

DAS28 scores will be interpreted using the following categorization:

- Remission: DAS28 \leq 2.6
- Low Disease activity: $2.6 < \text{DAS28} \leq 3.2$
- Moderate Disease Activity: $3.2 < \text{DAS28} \leq 5.1$
- High Disease Activity: DAS28 > 5.1

The full CRF is presented in Appendix C.

PRO questionnaires

The following PRO questionnaires will be included in the patient questionnaire packet.

Health Assessment Questionnaire Disability Index (HAQ DI)

The HAQ DI is a patient-reported questionnaire to assess functioning impacted by RA. It includes the categories of dressing and grooming, arising, eating, walking, hygiene, reach, grip and common daily activities. It asks patients about the amount of difficulty they experience in these activities as well as the use of aids and/or devices. The HAQ also has a numeric rating scale (NRS) (13) to assess pain on a scale from 0 to 10. Self-administered by the patient, the completion time is approximately 3-4 minutes. The full version of HAQ DI is presented in Appendix D.

Short Form (36) Health Survey (SF-36)

The SF-36 is a patient-reported questionnaire of patient health-related QoL. It measures generic health concepts relevant across age, disease, and treatment groups. There are 36 items in total and the recall period is the last 4 weeks. The SF-36 consists of eight scaled scores, which are the weighted sums of the questions in their section. Each scale is directly transformed into a 0-100 scale. Completion time for the SF-36 is approximately 10 minutes. The full version of SF-36 is presented in Appendix E.

EuroQol 5 dimension, 3 level quality of life questionnaire (EQ-5D-3L)

The EQ-5D-3L measures the patient's overall health state in a descriptive system of health-related QoL states consisting of five dimensions (mobility, self-care, usual activities, pain/discomfort, and anxiety/depression) each of which can take one of three responses. The responses record three levels of severity ('no problems', 'some problems', and 'extreme problems) within a particular EQ-5D-3L dimension (14,15). In addition, a VAS rates current health state between 0-100. The EQ-5D-3L results can be converted to health utility scores. Completion time for the EQ-5D-3L is approximately 2-3 minutes. The full version of EQ-5D-3L is presented in Appendix F.

Work Productivity and Activity Impairment (WPAI)

The WPAI is a patient-reported questionnaire to measure work and activity impairment during the past seven days. It determines employment status, hours missed from work due to the disease (i.e. RA), hours missed from work for other reasons, hours actually worked, the degree to which the disease affected work productivity while at work and the degree to which the disease affected activities outside of work. Additional questions around employment status will be incorporated into the survey. The completion time for the WPAI is approximately 2-5 minutes. The full version of WPAI is presented in Appendix G.

Patient Global Impression of Change (PGIC)

The PGIC measures the patient's perceptions of changes in their disease. It consists of one question asking about the change in their condition; for this study, the base will be "since you initiated your adalimumab treatment". The completion time for the PGIC is less than 1 minute. The full version of PGIC is presented in Appendix H.

Patient Treatment Satisfaction Questions

The patient treatment satisfaction questions were developed de novo for this study and are not considered "validated" questions. Self-administered by the patient, the completion time for the patient treatment satisfaction questions is approximately 1-2 minutes. The full version of patient treatment satisfaction questions are presented in Appendix I.

Healthcare Resource Utilization (HCRU) Questionnaire

The HCRU questionnaire will collect data on the healthcare resources consumed in the prior 3 months, as recall beyond 3 months may be problematic in an older population(16). HCRU collection will include data such as the number of physician visits and to which physician (GP, specialist), Emergency Department visits, hospitalizations, and other drugs

as well as devices and aids purchased to assist in their mobility due to RA. The HCRU questionnaire will be part of the patient questionnaire and will be distributed to patients together with the PRO questionnaires (Appendix D to Appendix I). The full HCRU questionnaire is presented in Appendix J.

All of the questionnaires will use the validated Korean version.

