 ₁₁ Naproxen (Naprosyn, Anaprox, Aleve)	_____	_____ mg	_____
 ₁₂ Celecoxib (Celebrex)	_____	_____ mg	_____
 ₁₃ Aspirin (ASA)	_____	_____ mg	_____
 ₁₄ Diclofenac (Voltaren)	_____	_____ mg	_____
 ₁₅ Indomethacin (Indocid)	_____	_____ mg	_____
 ₁₆ Others	_____	_____ mg	_____
Others			
 ₁₇ Steroids	_____	_____ mg	_____
 ₁₈ Stomach or gastric medications	_____	_____ mg	_____

Thank you for completing the Clinician Case Report Form.
Please return this form to the IMS representative.

Follow-up:

1023259 Real-World Impact of RA

Clinician Case Report Form (Follow-up)

All of the following information must be completed by the clinician or his/her representative.

Clinician name: _____

Clinician signature: _____

[figure not shown]
[figure not shown]
Today's date: / /

Please provide the information below.		
1. What is the patient's current disease status?	 Moderate	 Severe

1023259 Real-World Impact of RA

Site number	-	Participant ID
-------------	---	----------------

imshealth™
INTELLIGENCE APPLIED.

Please provide the information below.		
2. Please perform a swollen and tender joint examination on your patient using the figure below and record the total number of tender/swollen joints in the appropriate boxes on the right.	Tender Joint Count	Swollen Joint Count

If diagnosis is RA:
 
 
  
Tender ○ Mark If 'none'
 
 
  
Swollen ○ Mark If 'none'
 
 
		
3. Please record the most recent Erythrocyte Sedimentation Rate (ESR) (in mm/hour) or C-reactive protein (CRP) (in mg/L) of this patient.	 ESR (mm/hour) Test Date (DD/MM/YYYY): ____/____/_____	
	 CRP (mg/L) Test Date (DD/MM/YYYY): ____/____/_____	
4. Please record the latest DAS28 score*, if calculated		

* For calculation instruction, please refer to study protocol, page 21, clinical case report form (CRF).

1023259 Real-World Impact of RA

Site number	-	Participant ID
-------------	---	----------------

5. Please check all the surgeries this patient has received for her/his Rheumatoid Arthritis since the last completed survey.

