#### **5.5 Analysis Plan for Additional Secondary Objectives**

- Descriptive statistics will be presented for post-index overall RA related direct healthcare resource utilization (Excel Table 8)

- Consultations/visits to healthcare professionals for treatment of RA (number of patients with  $\geq 1$  visit; categorized by the treatment department listed in 3.5.4)
- Procedures received when visiting the healthcare professional(s) for treatment of RA (number of patients with  $\geq 1$  procedure; categories listed in 3.5.4)
- surgeries received when visiting the healthcare professional(s) for treatment of RA (number of patients with  $\geq 1$  surgery; categories listed in 3.5.4)
- Hospitalizations in relation to RA (number of patients with  $\geq 1$  admission)
- Length of stay in days (mean, SD, median)
- Concomitant medications taken for RA (number of patients with  $\geq 1$  medication; categories listed in 3.5.4))

- Associations between disease severity (measured by DAS28) and PROs (HAQ DI score, SF-36 domain scales, EQ-5D-3L index, WPAI outcomes) will be analyzed using the bivariate linear regression model (Excel Table 9.1). Separate models will be estimated to identify the association between DAS28 and each of the PROs.
- Additionally, in Excel Table 9.2, separate bivariate liner regression models will be estimated to identify the association between change in DAS28 and change in each of the PROs at 12 and 24 weeks after baseline respectively.

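### The Week 12 and Week 24 DAS28 may use an ESR or CRP taken before adalimumab was started, which can dilute the change-in-severity regressions (SAP Table 9.2)

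*Protocol*

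**What the plan says.** Protocol Table 1 schedules DAS28 at baseline, Week 12, Week 24 and early termination. Protocol 9.2.4.7 describes how the score is obtained: count swollen and tender joints, obtain ESR or CRP, and ask for the patient's global assessment. On the laboratory step it adds that "the latest measurement in the medical records may also be used if a blood draw is not standard for that visit". SAP 3.5.2 repeats the sentence. Neither document gives a maximum age for the value or a condition tied to the start of adalimumab.

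The follow-up CRF (Protocol Appendix C) has three relevant items:

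- Joint counts: "Please perform a swollen and tender joint examination on your patient".
- Laboratory marker: "Please record the most recent Erythrocyte Sedimentation Rate (ESR) (in mm/hour) or C-reactive protein (CRP) (in mg/L) of this patient", with a test date beside each marker.
- Total score: "Please record the latest DAS28 score*, if calculated". The readable form text shows no date for the score.

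The clinician's Early Termination Form (Appendix K) uses the same items.

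The only time window given concerns visits: "A ± 7 day window is permitted around scheduled study visits". Protocol 9.2.4.5 keeps the study within routine care: "Not additional task will be required other than current practice". A scheduled visit without a blood draw is therefore foreseeable, and 9.2.4.7 expressly provides for it.

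The follow-up scores feed SAP 5.5, where Table 9.2 estimates the "association between change in DAS28 and change in each of the PROs at 12 and 24 weeks after baseline respectively". SAP 3.5.5 rules out imputation apart from the missing day of a date and PRO items. It is silent on old laboratory values.

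**The concern.** If no marker was measured between baseline and the follow-up visit, the latest one on file is the pre-treatment value. Used as the rule allows, it gives a follow-up DAS28 whose laboratory term has not moved, beside a PRO completed that day. In effect this is an undeclared carry-forward in a plan that otherwise declines to impute. The test date that would reveal it is collected, but no rule uses it.

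The analysis at stake is the additional secondary objective on change in disease severity and change in PROs. Part of the DAS28 change would be zero by construction in some patients, and which patients would depend on how often their site draws blood.

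The CRF opens a second, less certain route. It asks for the latest total score and does not date it, so a site could enter an earlier one. The whole change would then be zero.

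**Working it through.** The documents give no figure on this point, so there is none to reproduce. The check has two parts.

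**1. Error in one patient's score.** Inputs: the weights in Protocol 9.2.4.7, 0.70 per unit of ln(ESR) and 0.36 per unit of ln(CRP). If the marker truly fell by a factor r, a carried-over pre-treatment value makes the follow-up score too high by 0.70 × ln(r) or 0.36 × ln(r).

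| True fall | ESR | CRP |
|---|---|---|
| 2-fold | 0.49 | 0.25 |
| 3-fold | 0.77 | 0.40 |
| 4-fold | 0.97 | 0.50 |

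SAP 3.5.2 prints a single formula with 0.70 for either marker. Under that formula the ESR column would apply to CRP as well. The two formulas need reconciling separately.

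**2. Effect on Table 9.2.** All inputs here are assumptions. Let the DAS28 change be a clinical part (joints and global assessment; mean −1.4, SD 0.9) plus an independent laboratory part (mean −0.5, SD 0.5; the mean is about an ESR halving). The total then has mean −1.9 and variance 0.81 + 0.25 = 1.06. A share f of patients has a stale value, at random. SAP 5.5 does not say which variable is the regressor, so both directions are shown.

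*Only the marker is stale.* The covariance with the PRO is proportional to 0.81 + (1 − f) × 0.25. The variance of the recorded change is 0.81 + (1 − f) × (0.25 + f × 0.25), where the second 0.25 is the squared mean, 0.5². With DAS28 change as predictor, the slope is multiplied by covariance/variance. As outcome, it is multiplied by covariance/1.06.

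| f | Covariance | Variance | Slope ratio, predictor | Slope ratio, outcome |
|---|---|---|---|---|
| 10% | 1.035 | 1.0575 | 0.979 | 0.976 |
| 30% | 0.985 | 1.0375 | 0.949 | 0.929 |
| 50% | 0.935 | 0.9975 | 0.937 | 0.882 |

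The loss is 2% to 6% with DAS28 change as predictor and 2% to 12% as outcome. A simulation of 400,000 patients with the same inputs and a true correlation of 0.50 agrees: the predictor slope goes from 0.243 to 0.238, 0.231 and 0.228, and the correlation to 0.49, 0.47 and 0.45.

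*The whole score is stale (change recorded as 0).* With mean m and variance s² of the true change, the predictor slope is multiplied by s²/(s² + f × m²).

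- m = −1.5, SD 1.2: 1.44/(1.44 + 0.225) = 0.865 at f = 10%; 1.44/(1.44 + 0.45) = 0.762 at f = 20%.
- m = −1.9, s² = 1.06: 1.06/(1.06 + 0.361) = 0.746 at f = 10%; 1.06/(1.06 + 0.722) = 0.595 at f = 20%.

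The loss is 14% to 41%, depending on the assumptions. With DAS28 change as outcome the multiplier is 1 − f, a loss of 10% or 20%.

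**The case against.** The strongest defence is that the allowance is deliberate. A non-interventional study cannot require blood draws, the marker's date is recorded, and the joint counts and global assessment are obtained for the visit. Only one term of the score can be old, and the calculation above shows that this matters little even at high frequency. That stands, and it limits the size of the point. It does not supply the missing condition: followed as written, the rule still admits a pre-treatment marker as a Week 12 or Week 24 value.

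A reader might infer more, and the documents do not support it in four respects.

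- **A slope loss of 14% or more.** That needs whole scores copied forward. Protocol 9.2.4.7 places the score after that visit's components, and the condition that it be calculated more naturally means leaving the item blank otherwise. Copying is not excluded, but it is not what the instruction describes.
- **Biased follow-up disease-activity categories.** SAP 5.2 tabulates DAS28 categories at baseline only, and the table list in SAP section 6 has no follow-up category table.
- **A distorted entry criterion or baseline severity.** A pre-treatment marker is what baseline should contain. Only its age could be questioned, and nothing in the documents shows that to be a problem.
- **That stale values will occur.** A visit without a draw does not mean that no test was done since baseline. The documents give no frequency.

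**Conclusion.** The point holds as a gap in a stated rule, with a limited reach. A pre-treatment ESR or CRP can legitimately enter a follow-up DAS28 and cancel the laboratory part of the change, for example 0.49 points if ESR truly halved. The exposed analysis is Table 9.2. The effect there is probably small if only the marker is stale, and larger if an undated total score is carried forward.

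The score errors follow from the protocol's own weights, given the assumed falls. The slope losses rest on assumed means, SDs and frequencies, and on staleness being unrelated to response. They show order of magnitude only.

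The primary paired t-test on HAQ DI does not use DAS28, and its sensitivity ANOVA uses baseline severity only. The point is still worth acting on, because the correction uses data already collected.

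**What to change.** Add to SAP 3.5.2 and 5.5, before the analysis:

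1. For Weeks 12 and 24, treat DAS28 as missing if the ESR/CRP test date is on or before the first adalimumab injection or the previous study visit. The day itself must be included: inclusion criterion 4 has adalimumab started at the baseline visit, so a baseline sample can carry the injection date.
2. Query absent test dates. Also query dates whose day was filled with 15 under SAP 3.5.5 where that day decides the result.
3. Where the components are available, derive DAS28 from that visit's components rather than from the entered score; otherwise query the score. The readable CRF text shows no field for the global assessment (figures are not visible), so check first whether derivation is possible.
4. Report the number of values excluded, by visit and site, and run Table 9.2 with and without them. If Table 9.1 includes follow-up visits, which SAP 5.5 does not say, do the same there.

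The cost is some additional missing DAS28 values, possibly concentrated at sites that draw blood less often, which is why both runs are needed. No extra blood draw is required, and the rule leaves the HAQ DI data intact. A window in days around each visit would be a further choice for which the documents give no basis. Rewording the CRF would come late, since data collection was to end on 28 February 2018; the SAP rule does not depend on it.
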